7.1 Assessment of Efficacy

The primary objective of this study is to assess the effect of letrozole versus placebo on the AaPO₂ in subjects with HPS at 6 months.

7.1.1 Alveolar-Arterial Oxygen Gradient

The AaPO₂ (assessed by seated arterial blood gas sampling while breathing room air) is the primary endpoint of this Phase II study for several reasons. The diagnosis of HPS is predicated on abnormal gas exchange, which normalizes after liver transplant. We have shown that interventions which decrease lung angiogenesis and intrapulmonary shunting in the animal model of HPS also improve AaPO₂. The AaPO₂ is strongly associated with the degree of intrapulmonary shunting by contrast TTE in HPS.

7.2 Secondary Outcome Measures

There are several secondary outcome measures of this study. They include:

- Difference in changes in intrapulmonary shunting between letrozole and placebo groups at 6 months
- Difference in changes in estradiol, progesterone, testosterone levels between letrozole and placebo groups at 3 months and 6 months
- Difference in changes in SF36 scores and mMRC dyspnea index scores between letrozole and placebo groups at 6 months
- Difference in changes in distance walked in six minutes between letrozole and placebo groups at 6 months
- Difference in changes in PaO₂ and oxygen saturation by pulse oximetry between letrozole and placebo groups at 3 months and 6 months
- To assess the effect of letrozole versus placebo on AaPO₂ at 3 months and 6 months
- Safety and side effects associated with letrozole administration in patients with HPS

7.2.1 Intrapulmonary Shunting

Intrapulmonary shunting will be assessed using contrast TTE in a standardized fashion. A decrease in arterio-venous dilations in the lungs with the administration of letrozole should be associated with a decrease in the degree of intrapulmonary passage of bubbles using agitated saline.

Additionally, we will use technetium macroaggregated albumin perfusion scans as a secondary quantification measure for shunting. A decrease in shunting should be associated with decreased passage of the radiotracer out of the lungs.

7.2.2 Six-Minute Walk Distance

Walking is the most basic form of exercise and is integral to daily activities. The 6MWT is a standardized, timed, submaximal test of unencouraged, self-determined distance walked which is reliable and valid. Standardized test methods with scripted and timed statements have been established in prior studies and will be followed. The 6MWT is non-invasive and safe will be

performed at baseline and 6 months. The subject will be instructed to wear comfortable clothing and shoes. The test will be performed at approximately the same time of day at each visit. The Borg score for dyspnea and oxygen saturation will be recorded at the beginning and conclusion of each test.

7.2.3 SF-36 / Modified Medical Research Council Dyspnea Scale

The SF-36 is one of the most widely used generic measures of subjective health status. The SF-36 includes one multi-item scale that assesses eight health concepts: 1) limitations in physical activities because of health problems; 2) limitations in social activities because of physical and emotional problems; 3) limitations in usual role activities because of physical health problems; 4) bodily pain; 5) general mental health (psychological distress and well-being); 6) limitations in usual role activities because of emotional problems; 7) vitality (energy and fatigue); and 8) general health perceptions. Subjects will complete the SF-36 at baseline, and 6 months.

The modified Medical Research Council (mMRC) Dyspnea Scale is an easy to use tool which can quantify the disability attributable to breathlessness. Symptom severity is graded from 0 (least severe) to 4 (most severe).

8 Statistical Plan

8.1 Study Design

The proposed project involves one primary and several secondary objectives. To address these aims we have devised a double-blind, randomized, placebo-controlled trial.

8.2 Sample Size, Effect Size, and Power Calculations

Our primary endpoint is change in A-a gradient over 6 months between the treatment and placebo groups. We expect 20 patients to enroll in this study. We have set $\alpha = 0.05$ and the standard deviation of change in AaPO₂ at ~ 10 mmHg. Assuming all this, we will have an 80% power to detect a 13.2 mmHg change in A-a gradient.

8.3 Disposition of Subjects and Baseline Comparisons

Summaries of all subjects screened, recruited, randomized, and the number who complete visits at 3 and 6 months post-randomization will be provided, according to the CONSORT guidelines. The treatment groups will be compared at baseline with respect to demographics and baseline measurements related to efficacy and safety without formal statistical testing.

8.4 Statistical Methods

8.4.1 Data Analysis

The intent-to-treat analysis will include all randomized subjects. Hypothesis testing will use two-sided α level 0.05 without correction for multiplicity. We will summarize demographics and baseline and follow-up endpoints.

8.4.2 Univariate Analysis

Continuous variables will be summarized by the mean, median, standard deviation, and range, as appropriate. We will use contingency tables for discrete and dichotomous variables.

8.4.3 Analysis of Treatment Assignment and Outcome Measures

The primary analysis will compare the absolute change from baseline to 6 months in AaPO2 between the blinded treatment arms using a two-sample t-test. This will be supplemented with mixed analysis of variance methods to allow inclusion of the baseline value (fixed) and clinical site (random). If the data are not normally distributed, they will be transformed. For dichotomous outcomes, logistic regression will be used. For secondary outcomes with additional longitudinal assessments, including results of the plasma biomarker assessments, 6MWT, SF-36, ABG, and the modified Medical Research Council Dyspnea Scale, linear mixed effects models or generalized estimating equations will be used as appropriate. All patients will be assessed for toxicity and included in the safety analysis. This analysis will include summaries of the incidence and grade of toxicities. Patients will be evaluated for serious adverse events. Safety interim analyses will be performed and reported at each continuing review with the IRB.

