Study Design	Randomized, double-blind, placebo-controlled parallel trial of 20 subjects with HPS. Eligible subjects will be randomly assigned 1:1 to receive either letrozole 2.5 mg orally daily or placebo for 6 months.
Number of Subjects	20 total subjects; 10 subjects at each site
Duration of Administration	6 months
Reference therapy	There is no reference therapy

Statistical Methodology	
Primary endpoint:
 
 • Difference in changes in AaPO₂ between letrozole and placebo groups at 6 months. 
Secondary endpoints:
 
 • Difference in changes in intrapulmonary shunting between letrozole and placebo groups at 6 months • Difference in changes in estradiol, progesterone, testosterone levels between letrozole and placebo groups at 3 months and 6 months • Difference in changes in SF36 scores and mMRC dyspnea scale scores between letrozole and placebo groups at 6 months • Difference in changes in distance walked in six minutes between letrozole and placebo groups at 6 months • Difference in changes in PaO₂ and oxygen saturation by pulse oximetry between letrozole and placebo groups at 3 months and 6 months • To assess the effect of letrozole versus placebo on AaPO₂ at 3 months and 6 months • Safety and side effects associated with letrozole administration in patients with HPS 
Sample size and power:
 
A total of 20 patients will be enrolled (10 letrozole, 10 placebo), which will provide 80% power to detect a 13.2 mm Hg difference in changes in AaPO₂ ($\alpha = 0.05$).
 
Data analysis:
 
The primary analysis will compare the absolute change from baseline to 6 months in AaPO₂ between the blinded treatment arms using a two-sample t-test. Incidence of adverse events and secondary endpoints will also be analyzed.

-------------------------	---

1 Introduction

This document is a protocol for a human research study. This study will be carried out in accordance with the applicable United States government regulations as well as research policies and procedures of both Mayo Clinic and the University of California, San Francisco.

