4.1 Inclusion Criteria

- ≥ 18 years old
- Diagnosis of moderate to very severe hepatopulmonary syndrome:
 - o Presence of liver disease or portal hypertension
 - o Intrapulmonary shunting on contrast-enhanced echocardiogram
 - o Hypoxemia [A-a gradient ≥ 15 mmHg (or ≥ 20 mmHg if age > 64) and PaO₂ < 80 mmHg on arterial blood gas testing]
- Child-Pugh class A or B liver disease
- MELD score < 20

- ≥ 18 years old
- Female subjects must be post-menopausal (defined as 12 months of spontaneous amenorrhea or 6 weeks postsurgical bilateral oophorectomy without or without hysterectomy)
- Ability to provide informed consent

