6.1 Study Visits

6.1.1 Informed Consent

Eligible subjects meeting the inclusion/exclusion criteria will be referred if there is interest in enrolling. The following procedures will be performed during the screening process:

- Sign and date the informed consent and HIPAA release
- Review of the inclusion/exclusion criteria
- Schedule a screening visit

After the subject has consented, the subject will be scheduled for a baseline visit within 60 days. If the baseline visit is not scheduled within the first 2 weeks following the informed consent, the research coordinator will send a reminder letter to the subject. The coordinator will also request that the subject refrain from smoking for 12 hours prior to the study visit. Visit 1: Baseline

Baseline information will be used to characterize the participants and to compare the experimental groups with regards to demographics and other variables. Safety laboratories, ABG, and contrast TTE obtained at the screening visit will be used as baseline measurements. Eligibility criteria will be reviewed prior to randomization to treatment group.

The research coordinator will remind the subject to avoid heavy exercise for 12 hours prior to the study visit. The coordinator will also request that the subject refrain from smoking for 12 hours prior to the study visit.

The following procedures will be performed within 60 days of consent, during the baseline visit and after evaluation of this data, the investigator will determine they are eligible to enroll in the trial:

- Review of inclusion/exclusion criteria
- Labs/Phlebotomy: complete blood count with differential, including hemoglobin, hematocrit, and platelet count, complete metabolic panel, and coagulation studies, lipid panel, estradiol, progesterone, testosterone, sample for storage for future studies; stored samples will only apply to the 10 Mayo participants. Values can be obtained from last 90 days
- Arterial blood gas (while seated while breathing room air) Values can be obtained from last 90 days.
- Spirometry and lung volumes (if not performed within the prior 3 years)
- Contrast echocardiogram. Values can be obtained from last 365 days.
- Technetium macroaggregated albumin perfusion scan Values can be obtained from last 365 days.
- DEXA scan Values can be obtained from last 365 days.
- Review of medical history
- Review current medications
- Vital signs
- Physical exam Values can be obtained from last 90 days.

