6.3 Visit 4: 6 Month Visit (+/- 30 day window)

The research coordinator will remind the subject to avoid heavy exercise for 12 hours prior to the study visit. The coordinator will also request that the subject refrain from smoking for 12 hours prior to the study visit.

The subject will arrive at the study site outpatient clinic. The following procedures will be performed:

- Labs/Phlebotomy: complete blood count with differential, including hemoglobin, hematocrit, and platelet count, complete metabolic panel, and coagulation studies, lipid panel, estradiol, progesterone, testosterone, sample for storage for future studies; stored samples will only apply to the 10 Mayo participants.
- Arterial blood gas (while seated while breathing room air)
- Technetium macroaggregated albumin perfusion scan

- Review of medical history
- Review current medications
- Vital signs
- Contrast echocardiogram
- Physical exam
- Modified Medical Research Council Dyspnea Scale assessment
- SF-36 questionnaire assessment
- 6 minute walk distance with Borg Score

Blood samples for study assays will be processed and/or banked.

After all these studies have been completed, the investigator or research coordinator will take an interim medical history and perform a physical examination including vitals, review current medications, and complete the mMRC Dyspnea Scale assessment.

The research coordinator will thank the subject for his or her participation. The coordinator will contact the clinician 24 hours after the study visit to discuss the clinical lab results.

Test	Baseline	1 month	3 months	6 months
History	X	X	X	X
Modified Medical Research Council (mMRC) Dyspnea Scale	X	X	X	X
Assessment of adverse effects-		X	X	X
Assessment of compliance		X	X	X
Physical examination, including vital signs	X	X**	X	X
Room air arterial blood gas in seated position	X		X	X
Laboratory Data*	X		X	X
SF-36	X			X
Contrast-enhanced echocardiogram	X			X
Technetium macroaggregated albumin perfusion scan	X			X
6 minute walk distance with Borg Score at baseline and completion	X			X
Complete pulmonary function tests if not performed within 3 years (spirometry, lung volumes and diffusion capacity)	X			
DEXA Scan	X			
Dispense study medication	X		X	

* Laboratory data to include complete blood count, complete metabolic panel, lipid panel, PT/INR, estradiol, progesterone and testosterone levels and stored samples for future analysis.

** If in-clinic visit

7 Assessment of Efficacy and Outcome Measures

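### The primary t-test of change in AaPO₂ is valid and adequately described, but putting baseline AaPO₂ into the primary model is a cheap improvement whose size the documents do not fix

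*Combined protocol and SAP*

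**What the plan says.** The Study Summary (Statistical Methodology) and section 8.4.3 agree on the primary analysis. Section 8.4.3 says that it "will compare the absolute change from baseline to 6 months in AaPO2 between the blinded treatment arms using a two-sample t-test". The Study Summary describes a comparison of the "absolute change from baseline to 6 months in AaPO₂ between the blinded treatment arms using a two-sample t-test". Section 8.4.3 then adds: "This will be supplemented with mixed analysis of variance methods to allow inclusion of the baseline value (fixed) and clinical site (random"). So a baseline-adjusted analysis is planned, but as a supplement and together with site.

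The power statement in section 8.2 takes "the standard deviation of change in AaPO₂ at ~ 10 mmHg". With 20 patients it claims 80% power for 13.2 mmHg. Section 8.4.1 sets a two-sided 5% level.

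Baseline AaPO₂ should exist for every randomized patient, because eligibility requires an "A-a gradient ≥ 15 mmHg (or ≥ 20 mmHg if age > 64") (section 4.1). Section 6.1.1 states: "Safety laboratories, ABG, and contrast TTE obtained at the screening visit will be used as baseline measurements". For that baseline it allows: "Arterial blood gas (while seated while breathing room air) Values can be obtained from last 90 days". The final measurement falls at "Visit 4: 6 Month Visit (+/- 30 day window").

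The documents give no baseline SD, no 6-month SD, no correlation between the two times and no dropout rate.

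**The concern.** With 10 patients per arm, the arms may differ in baseline AaPO₂ by chance. If patients with a high baseline tend to fall more, a t-test of change carries that imbalance into the treatment estimate. Adjusting for baseline removes it and usually narrows the confidence interval. Here the covariate costs nothing to collect and the plan already regards it as worth modelling. However, the adjusted model is not the one that decides the primary conclusion. If the two analyses disagree, the unadjusted one stands.

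At stake is some power and precision in a very small trial, and how far the primary result depends on the luck of the allocation.

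**Working it through.** **1. The plan's own figure.** Inputs: difference 13.2 mmHg and SD of change 10 (section 8.2), 10 per arm (Study Summary), two-sided 0.05 (section 8.4.1).

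- Standard error = 10 × √(2/10) = 4.47 mmHg.
- Noncentrality = 13.2 / 4.47 = 2.95, with 18 degrees of freedom.
- Noncentral t power = 79.7%. The difference detectable with exactly 80% power is 13.25 mmHg, and the mean 95% CI half-width is 9.27 mmHg.

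The stated 80% is reproduced.

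**2. Adjusted analysis, as a function of c.** Adding baseline has three effects:

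- The residual SD becomes 10 × √(1 − c²).
- The residual degrees of freedom fall from 18 to 17.
- The variance is multiplied by 1 + T²/18, where T is the standardized chance baseline difference and follows a t distribution on 18 df.

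Power is the noncentral t probability with noncentrality 13.2 / [10√(1 − c²) × √(0.2(1 + T²/18))], averaged over T. With c assumed:

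| \|c\| | Power | Change vs t-test (points) | CI half-width (mmHg) | Detectable at 80% (mmHg) |
|---|---|---|---|---|
| 0 | 77.1% | −2.6 | 9.57 | 13.69 |
| 0.2 | 78.7% | −1.0 | 9.38 | 13.41 |
| 0.25 | 79.7% | 0.0 | 9.27 | 13.26 |
| 0.3 | 80.8% | +1.1 | 9.13 | 13.06 |
| 0.4 | 83.8% | +4.1 | 8.77 | 12.55 |
| 0.5 | 87.6% | +7.9 | 8.29 | 11.86 |
| 0.6 | 92.0% | +12.3 | 7.66 | 10.95 |

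Break-even is at |c| = 0.252. Simulation of 400,000 trials per setting agrees: −2.6 points at c = 0, 0.0 at 0.25, +1.1 at 0.3 and +7.9 at −0.5. The largest loss at any true difference is 2.75 points, near 11.75 mmHg.

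**3. Fewer evaluable patients.** Section 8.4.5 describes a completers analysis and no dropout rate is stated, so 9 and 8 per arm are shown as assumptions.

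| Evaluable per arm | t-test | Adjusted, \|c\| = 0 to 0.6 | Loss at c = 0 (points) | Break-even \|c\| |
|---|---|---|---|---|
| 9 | 74.8% | 71.7 to 88.5% | 3.1 | 0.27 |
| 8 | 69.0% | 65.3 to 83.5% | 3.7 | 0.29 |

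**4. What c might be.** Let r be the baseline to 6-month correlation and k the 6-month SD divided by the baseline SD. Then c = (rk − 1) / √(1 + k² − 2rk). With equal SDs this is −√((1 − r)/2), so break-even is at r = 1 − 2 × 0.252² = 0.87. Adjusted power at 10 per arm, rounded to whole percent, against 79.7% for the t-test:

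| k | r = 0.3 | 0.5 | 0.7 | 0.8 | 0.9 | Loss when r is |
|---|---|---|---|---|---|---|
| 0.9 | 94 | 91 | 88 | 86 | 85 | never |
| 1.0 | 92 | 88 | 83 | 81 | 79 | above 0.87 |
| 1.1 | 89 | 85 | 80 | 78 | 77 | 0.73 to 0.97 |
| 1.25 | 86 | 82 | 78 | 77 | 79 | 0.59 to 0.91 |
| 1.5 | 82 | 79 | 77 | 79 | 86 | 0.43 to 0.82 |

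The documents point both ways. The two blood gases can be about 5 months apart (6 months − 30 days) or about 10 months apart (6 months + 30 + 90 days), and a long gap tends to lower r. The wide range of disease severity admitted tends to raise r. The entry threshold trims low baselines and so tends to push k above 1, which reduces the gain.

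**5. Chance imbalance.** If the letrozole arm starts one standard error lower or higher, the expected difference in change moves by c × 4.47 mmHg. For c = −0.5 that is 2.24 mmHg, giving 10.96 or 15.44 instead of 13.2.

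| Assumed k, r | c | t-test power, lower / higher start | Adjusted power |
|---|---|---|---|
| 1.0, 0.5 | −0.50 | 66 / 93% | about 88% either way |
| 1.0, 0.8 | −0.32 | 71 / 88% | about 81% either way |
| 1.25, 0.7 | −0.14 | 76 / 83% | 78% on average |
| 1.25, 0.8 | 0 | 80 / 80% | 77% on average |

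When c is near 0 there is little or no dependence to remove.

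**The case against.** The strongest reply is that nothing is wrong. The t-test is prespecified, matches the power statement and is valid under randomization: simulated type I error is 4.9 to 5.2% for both tests. An adjusted model is already planned. All of that stands. A reader might infer that the primary test is biased or that the power claim fails because baseline is left out, and the documents support neither. The 66/93% pair is variation around the stated 80%, not bias. What the reply does not answer is that the supplementary model has no say in the primary conclusion.

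The second reply is that the sign of the benefit is unknown. This also stands. A reader might infer that adjustment is bound to gain power. For k of 1.1, 1.25 and 1.5 at r = 0.7, 0.8 and 0.9, seven of the nine cells fall below the t-test. The average gain can also be modest: at r = 0.7 with equal SDs it is nearly 4 points, about what is lost if the SD of change is 10.5 rather than 10 (t-test power 75.8%). The case for changing rests on asymmetry: a small bounded loss against a possibly larger gain.

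The third reply concerns timing. The analysis plan sits inside the protocol, so the change is an amendment. Section 5.7 leaves the statistical analyst unmasked, so changing the primary test after outcomes by arm are visible would invite a charge of selection. This is correct and limits when the fix is acceptable.

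**Conclusion.** The point holds as an efficiency improvement worth considering, with medium confidence. The plan contains no error here.

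At the design values (difference 13.2 mmHg, SD of change 10, 10 evaluable per arm, normal data), adjustment ranges from a 2.6-point loss at c = 0 to a 12-point gain at |c| = 0.6. The 2.6-point figure is not a general ceiling, because the loss is slightly larger at other true differences and grows as evaluable numbers fall. The protection against chance imbalance is real when c is clearly away from 0 and disappears as c approaches 0. The values of c, r and k are all assumptions, and only data on repeated AaPO₂ in similar patients can narrow the range.

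**What to change.** Before anyone has access to outcome data by arm, amend the Study Summary and section 8.4.3 as follows:

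- Make the primary analysis a linear model of month-6 AaPO₂ (or its change) on treatment and baseline AaPO₂, reporting the adjusted difference and 95% CI in mmHg.
- Keep the two-sample t-test as a sensitivity analysis.
- Keep site in the supplementary model. Section 4.4 describes blocking for balance over time but does not say it is done within site. With equal SDs, r = 0.5 and no site effect, adding a fixed site term when arms are not balanced within site lowers simulated power from about 88% to 85%.
- In section 8.2, record the baseline SD and r (or c), ideally from the data behind the SD of about 10 mmHg. If they show |c| well below 0.25, keeping the t-test with that reason on record is sound.

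The cost is a protocol amendment submitted to the IRB (section 11), one residual degree of freedom, and a small power loss if |c| turns out below about 0.25. No patient, visit or procedure changes. If outcome data by arm have already been seen, leave the t-test as primary.

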3.2 Number of Subjects

A total of 20 subjects will be enrolled. Each site will enroll 10 patients.

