4.4 Randomization

Randomization will be blocked to ensure balance over time. The Research Pharmacy at Mayo Clinic and the University of California, San Francisco will prepare the prescriptions.. At the baseline visit, when the research coordinator registers the patient as meeting all inclusion/exclusion criteria, the patient can pick up that medication at the Research Pharmacy .

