10.5 Data Management

We will use REDCap, a validated secure HIPAA compliant database for data management.

Data Processing

As this is a two center study, all data collected will be entered into REDCAP by a study coordinator or co-investigator.

Data Security and Confidentiality

Research data will be stored with a code rather than any patient identifiers to protect patient confidentiality. All protected health information and the key to link patient identifiers to the sample code will be contained in REDCap, a secure web-based HIPAA compliant database that will only be accessible by study personnel authorized by the investigator.

Data Quality Assurance

Double data entry will be used and random data will be cross-checked and validated by the PI with source document verification.

Data Clarification Process

Data will be cross-checked with CRFs and the EMR for any data queries.

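### The supplementary model treats clinical site as random with only two sites, so its site adjustment rests on one degree of freedom and may be absent or only partial (minor)

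*Combined protocol and SAP*

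**What the plan says.** Section 8.4.3 makes the primary analysis a comparison of change in AaPO2 "between the blinded treatment arms using a two-sample t-test". That test has no baseline or site term. The section then adds mixed analysis of variance methods "to allow inclusion of the baseline value (fixed) and clinical site (random"). It does not name an estimator, a degrees-of-freedom method, or what to do if the site variance is estimated as zero.

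The number of sites is fixed at two. Section 3.2 states: "A total of 20 subjects will be enrolled. Each site will enroll 10 patients". Section 10.5 (Data Management) also describes a two-center study.

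On allocation, the Study Summary gives a 1:1 ratio, and Section 4.4 says only "Randomization will be blocked to ensure balance over time". Stratification by site is not stated. Tests are two-sided at 0.05 (Section 8.4.1).

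**The concern.** A random site effect treats the two centers as draws from a population of centers and asks the data for the variance of that population. Two centers supply one contrast, and one contrast says almost nothing about a variance.

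In a fit that estimates the variance and bounds it at zero, there are two outcomes. If the estimate is zero, the site term drops out and the model adjusts for baseline only. If it is positive, site is adjusted for in part, to a degree set by that single noisy contrast.

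The model was added in order to account for baseline and site. At stake is whether it reliably does the second of these. The question has some substance because within-site balance of the arms is not guaranteed: stratification by site is not stated, and the completers analysis in Section 8.4.5 can disturb whatever balance there is.

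**Working it through.** **Inputs from the documents.** 20 patients, 10 per arm and 10 per site, two sites; SD of change about 10 mmHg and design difference 13.2 mmHg (Section 8.2); two-sided α 0.05 (Section 8.4.1).

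**Assumptions.** The documents give no between-site SD, so a range of 0 to 10 mmHg is used. A REML-type fit is assumed. The residual SD is set at 10 mmHg.

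**1. The plan's own figure.** Two-sample t-test, 10 per arm, 18 df: the noncentrality is 13.2 / (10 × √(1/10 + 1/10)) = 13.2 / 4.472 = 2.95, and the critical t is 2.101. Power is 79.7%, which reproduces the stated 80%. No site term enters this calculation.

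**2. Chance of a zero site variance.** In a balanced layout with 10 per site, the site mean square has 2 − 1 = 1 df and expectation σ² + 10σ_s². The error mean square has 20 − 4 = 16 df after intercept, treatment, baseline and site. The variance estimate is zero when F = MS(site)/MSE is below 1. With k = 1 + 10σ_s²/σ², P(zero) = P(F[1,16] < 1/k).

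| Site SD (mmHg, assumed) | k | P(site variance estimated as zero) |
|---|---|---|
| 0 | 1.0 | 67% |
| 1 | 1.1 | 65% |
| 2 | 1.4 | 59% |
| 3 | 1.9 | 52% |
| 5 | 3.5 | 40% |
| 7.5 | 6.6 | 30% |
| 10 | 11.0 | 23% |

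The probability crosses one half at a site SD of about 3.3 mmHg. A REML simulation agrees: 65–67%, 53%, 41–42% and 24–26% at site SD 0, 3, 5 and 10. It used 1,200 runs per setting, with an assumed baseline SD of 10 and slope of −0.3.

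**3. When the estimate is positive.** The estimated share of the site contrast that is removed is 1 − 1/F. An observed F of 2 removes half of it. The 95% interval for the site variance has a lower limit of zero unless F exceeds about 6.1.

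**4. Effect on the treatment comparison (same simulation).**
- Mean absolute difference between the random-site and fixed-site treatment estimates: about 0.1 mmHg with arms balanced within site; about 0.4–0.5 mmHg otherwise (90th percentile 0.9–1.3).
- Type I error: 4–7% with random site and 4–6% with fixed site, using 16 df for both. The simulation error is about 0.6 points.

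**5. Price of a fixed site term.** Holding the SD at 10, power for 13.2 mmHg is 79.4% at 17 df (critical t 2.110) and 79.1% at 16 df (critical t 2.120). In the simulation, where treatment can be correlated with baseline and site, the fixed-site model rejected 0.8 to 2.6 points less often than the random-site model at a true difference of 13.2 mmHg (75–76% against 76–78%). Its type I error was also 0.1 to 0.9 points lower.

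**The case against.** The strongest reply is that little depends on this model. It is a supplement, the primary test contains no site term, and no decision rule uses the mixed model. A treatment estimate that moves by a few tenths of a mmHg is trivial beside a design difference of 13.2 mmHg. All of that stands, and it is why the point is minor.

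Second, the section names no estimator. In a classical additive mixed analysis of variance, site stays in the table and treatment is tested against residual error on 16 df, exactly as with a fixed site term. Truncation at zero belongs to REML-type fits. This also stands. The criticism is conditional on such a fit, which the wording permits but does not require.

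Three stronger readings are tempting, and the documents do not support them:

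- A reader might infer that the site adjustment will usually disappear. That is true only if the site SD is below about 3.3 mmHg, and the documents give no site SD. The 67% figure applies when the sites do not differ, which is the case in which losing the term matters least.
- A reader might attach the one-df chi-square factors, 0.45 to 32, to the site SD. They belong to the square root of the site mean square, which also contains residual variance. The site SD is indeed very imprecise, but that is not its interval.
- A reader might infer that the trial's main result or its error rate is compromised. The primary t-test has no site term, and the simulated type I error of the supplementary model stays close to 5%.

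What survives is that a prespecified adjustment may not be made, or may be made only in part, and that the plan does not say what happens then.

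**Conclusion.** The point holds as a minor specification flaw in a supporting analysis. With two sites, whether and how far the supplementary model adjusts for site depends on one contrast. Under a REML-type fit and a residual SD of 10 mmHg, the adjustment is lost altogether in roughly a quarter to two thirds of trials across assumed site SDs of 10 down to 0 mmHg. Otherwise it is partial and poorly determined.

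The usual shift in the treatment estimate is 0.1 to 0.5 mmHg, depending on within-site balance. That size rests on the assumed baseline SD, slope and site SDs, none of which the documents supply. The zero-variance probabilities rest on the assumed site SD and on 10 evaluable patients per site. The one-df statement needs only the two-site design.

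**What to change.** In Section 8.4.3, specify the supplementary model as a linear model for 6-month AaPO2 (or its change) on treatment, baseline AaPO2 and site, with site as a fixed effect and treatment tested against residual error. The two choices of outcome give the same treatment estimate once baseline is in the model. Site is then always adjusted for, including when the arms are unbalanced within site, and no rule for a zero variance is needed.

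The cost is a small change of wording and one error degree of freedom. If the arms are unbalanced within site there is also a small loss of precision. For example, with 6 letrozole and 4 placebo at one site and the reverse at the other, the arm–site correlation is 0.2, so the variance rises by a factor of 1/(1 − 0.04) = 1.04. Inference to a wider population of sites is given up, but two sites could not have supported it. The primary t-test and the sample size need no change.
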